- Pregnant participants will receive a 75-g oral glucose tolerance test during 24-28 gestational weeks, and GDM will be diagnosed if any of the following criteria are met, based on the recommendations of the International Association of the Diabetes and Pregnancy Study Groups Consensus Panel: fasting glucose ≥ 5.1 mmol/L, 1-hour glucose ≥ 10.0 mmol/L, or 2-hour glucose ≥ 8.5 mmol/L.
- Time Frame: during 24-28 gestational weeks.
- Type: binary variable (Yes / No).

(8) Maternal gestational weight gain (kg)

- This outcome will be calculated as body weight at delivery minus weight before pregnancy (self-reported).
- Time Frame: from pre pregnancy to delivery.
- Type: continuous variable.

(9) Maternal weight gain (kg) at early gestation

- This outcome will be calculated as body weight at around 20 gestational weeks minus weight before pregnancy (self-reported).
- Time Frame: from pre pregnancy to 20 gestational weeks.
- Type: continuous variable.

(10) Occurrence of gestational hypertension

- Pregnant participants will undergo blood pressure measurements at each prenatal visit. Gestational hypertension will be diagnosed if systolic blood pressure ≥ 140 and/or diastolic blood pressure ≥ 90 mmHg, based on the recommendations of the International Society for the Study of Hypertension in Pregnancy (ISSHP).
- Time Frame: during pregnancy.
- Type: binary variable (Yes / No).

- (11) Maternal body weight (kg) at 6 months after delivery (Continuous variable)
- (12) Maternal HbA1c (%) at 6 months after delivery (Continuous variable)
- (13) Infant body weight (g) at birth, 42 day, 3 months, and 6 months (Continuous, repeated measurements)
- (14) Infant length (cm) at birth, 42 day, 3 months, and 6 months (Continuous, repeated measurements)
- (15) Infant body mass index (kg/m²) at birth, 42 day, 3 months, and 6 months (Continuous, repeated measurements)
- (16) Medical cost that relates with fetus and birth defects during pregnancy and after birth (Time Frame: from confirmation of pregnancy to one year old after birth) (Continuous variable)

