3.3. Interventions

Experimental interventions: usual care plus additional procedures

- Before conception:

Participants will be examined for serum and RBC folate concentrations at enrollment to identify those with insufficient RBC folate concentration (<400ng/mL). Based on reviewing of folate supplement status of from the participant-administered questionnaire, a trained nurse will call the participant to inform them the RBC folate concentration and folate metabolism ability evaluated by one's genotypes of MTHFR C677T variant, and provide individualized folic acid supplementary instructions to improve folate status before get pregnant. A second RBC folate test is booked.

- During gestation -- Green channels for confirmation of fetus defects and a following genetic and clinical consulting:

In the both arms, fetus and infants with screen positive of fetus defect(s) will be referred via a green channel to approach an authorized tertiary obstetric hospital to achieve timely further routine comprehensive assessments and confirmative diagnosis. Then the participants with established diagnosis of fetus defects will be referred to a multi-discipline paediatric expert team for a deep consultation about possible postnatal treatments in the future to avoid unnecessary abortions.

- **After delivery:**

The participants from the experimental arm will additionally provide timely referral to a prespecified team of pediatrician experts for timely medical treatment or scheduled follow-up.

Standard tertiary interventions of birth defects (control arm, usual care):

Couples eligible for reproductive policy are entitled to routine health cares including general health cares (health education, medical history inquiry, physical examinations, consulting guidance and pregnancy outcome follow-up) and medical examinations (laboratory examinations, virus screenings and image examinations). But nutrients status is not included in these examinations, such as folate, vitamin B12 and microelements, etc. Regular antenatal cares are required, such as deformity screening by ultrasound. Routine neonatal screenings are conducted to diagnose infant with birth defect(s) timely.

Intervention procedures of FOID study

	Experimental arm Procedures in addition to the usual care	Control arm Usual care
Before conception		
Preconception at enrollment	RBC folate test Inform and instruction about folic acid supplementation via phone interview	Routine physical examination and routine blood tests

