3.5. Sample Size

Sample size calculation was performed based on the primary outcome- the incidence of a composite rate of fetus, still birth, or birth defects. The proportion of primary endpoint was conservatively estimated to be 8% in the control arm according to two recent observational studies^{6,7} and 4% in the experimental arm (or 50% reduction) based on the findings of a meta-analysis of randomized intervention trials of folic acid supplementation intervention in folate-deficient population⁸. With cluster size of 100 subjects per centre, K coefficient of 0.23, a power of 85 % and a 5 % level of type I error, 22 clusters (2200 patients or 1100 in each arm) will be required. To allow for a 10 % dropout rate, at least 111 subjects (2446 patients or 1223 in each arm) will be recruited in each centre.

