5.2. Secondary Outcome Analysis

All secondary outcomes will be analysed as a superiority design and two-sided 95% CIs for the treatment differences in these outcomes between the two arms will be calculated and presented. Secondary outcome analyses will be based on the ITT population unless specified.

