5.2.2. Analysis of continuous secondary outcomes

The continuous outcome will be summarised using number of subjects (n), mean, standard deviation (SD), minimum, and maximum by intervention group, and will be analysed by a GEE model with treatment as fixed effect, centre as cluster effect. The distribution will be normal distribution and link function is identity. Mean differences of outcome with their two-sided 95% CI between the two arms will be derived from the GEE model.

For repeated measurement variables, such as infant body weight at different visit, or maternal body weight during gestation, will be analyzed using linear mixed model with treatment, visit, interaction between treatment and visit as fixed effects, baseline measurement as covariate, cluster, and subject as random effects. SAS PROC GLMMIX will be used the data analysis.

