7. TABLE CONTENTS

Table 1: Summary statistics of baseline information.

Variable	Statistics	Treatment A (N=)	Treatment B (N=)	All (N=)
Age (year)	n			
	Mean			
	SD			
	<35			
	≥35			
Ethnicity	n			
	Han			
	Other			
Preconception Body Mass Index, kg/m ²	n			
	Mean			
	SD			
	<24 kg/m ²			
	≥24 kg/m ²			
Parity, time	n			
	1			
	≥2			
Presence of adverse pregnant history	n			
	Yes			
	No			
Exposure to smoking	n			
	Yes			
	No			

Table 2: Summary statistics of compliance of participants.

Variable	Statistics	Treatment A (N=)	Treatment B (N=)	All (N=)
RBC folate concentration before pregnancy	n			
	Mean			
	SD			
	Median			
	IOR			
<400 ng/ml	n(%)			
≥400 ng/ml	n(%)			
RBC folate concentration at the first antenatal visit	n			
	Mean			
	SD			
	Median			
	IQR			
<400 ng/ml	n(%)			
≥400 ng/ml	n(%)			

Table 3: Summary statistics of primary and secondary outcomes estimated by GEE model.

Primary and secondary binary outcomes	N(%)		GEE model analysis	
	Treatment A (N=)	Treatment B (N=)	Risk Ratio (95%CI)	p-value
Occurrence of fetus defects, still birth, and birth defects				
Occurrence of fetal defects				
Occurrence of birth defects				
Occurrence of abortion that related with congenital defects				
Occurrence of gestational hypertension				
Occurrence of maternal gestational diabetes				

Table 4: Summary statistics of secondary repeated measured outcomes estimated by linear mixed model.

Secondary repeated measured outcomes	Visit	n, mean (SD)		Mixed model analysis		
		Treatment A (N=)	Treatment B (N=)	A vs. B Mean difference (95%CI)	p-value	P-value from Treatment*time interaction test
Baby body weight	Birth					
	42 days					
	3 months					
	6 months					
Maternal body weight during gestation	Periconception					
	Gestational week 20					
	At delivery					

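### The baseline covariate in the mixed model is undefined and overlaps with the response visits; if it is birth size, any arm difference present at birth is subtracted from every infant estimate.

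*SAP*

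**What the plan says.** SAP section 5.2.2 states that repeated variables, "such as infant body weight at different visit, or maternal body weight during gestation, will be analyzed using linear mixed model". The terms of that model are treatment, visit, "interaction between treatment and visit as fixed effects, baseline measurement as covariate, cluster, and subject as random effects". The section does not say which measurement is the baseline for which outcome.

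Section 2.2.2, outcome (13), is "Infant body weight (g) at birth, 42 day, 3 months, and 6 months (Continuous, repeated measurements". Outcomes (14) and (15), infant length and BMI, have the same four visits and the same label.

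The shell "Table 4: Summary statistics of secondary repeated measured outcomes estimated by linear mixed model" has rows for infant weight at Birth, 42 days, 3 months and 6 months, and for maternal weight at Periconception, gestational week 20 and delivery. Each row calls for an arm difference with a confidence interval from the mixed model.

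On timing, section 3.3 has the nurse in the experimental arm "provide individualized folic acid supplementary instructions to improve folate status before get pregnant". For mothers, outcome (8) shows that a starting weight exists: it is defined as "body weight at delivery minus weight before pregnancy (self-reported".

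**The concern.** A baseline covariate helps when it is measured before treatment can act and is not itself one of the responses. For infants neither condition can be met. Nothing is measured on the infant before birth, so the only candidate is the first response visit, and that visit comes after the preconception intervention.

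If birth size is used, the Birth row regresses birth size on itself, and the later rows compare infants at equal birth size. Neither is the between-arm difference that section 5.2 promises ("two-sided 95% CIs for the treatment differences in these outcomes between the two arms will be calculated and presented"). The infant-weight rows of Table 4, and the matching analyses of length and BMI, could then understate or reverse a real difference.

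For mothers, Periconception weight is a plausible baseline. The fault there is only that it would stand on both sides of the model.

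**Working it through.** The SAP gives no figure for this model, so there is none to reproduce. The check is algebra plus an illustration.

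**Algebra.** Take complete data, a subject random intercept, treatment × visit, and one common slope β on birth value Y_0. Let d_t be the raw arm difference at visit t and d_0 the difference at birth. The estimated effects are:

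- visit t: d_t − β·d_0
- Birth, when it is also a response: d_0 − β·d_0 = (1 − β)·d_0
- change in effect from Birth to visit t: (d_t − β·d_0) − (d_0 − β·d_0) = d_t − d_0, which does not involve β

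Here β is the within-arm slope of the infant's mean response on Y_0. That is the average over response visits of corr(Y_t, Y_0)·SD_t/SD_0, with the Birth term equal to 1. A mixed-model fit to one simulated set of 300 infants gave effects of 33.8, −46.0, −76.6 and −99.2 g with β = 0.807. The closed form gave the same values.

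**Inputs.** From section 3.5, "22 clusters (2200 patients or 1100 in each arm) will be required", so 2200 infants are simulated. Not in the SAP, and therefore assumed: SDs of 420, 550, 750 and 950 g, and correlations of birth weight with the three later weights of 0.40/0.30/0.20 (low), 0.60/0.45/0.35 (middle) and 0.75/0.60/0.50 (high). Cluster effects were left out.

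**β with Birth among the responses**

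- Low: (1 + 0.52 + 0.54 + 0.45)/4 ≈ 0.63
- Middle: (1 + 0.79 + 0.80 + 0.79)/4 ≈ 0.85
- High: (1 + 0.98 + 1.07 + 1.13)/4 ≈ 1.05

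**Mean estimates over 400 simulated trials (g; Birth / 42 days / 3 months / 6 months)**

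| True effect | Low | Middle | High |
|---|---|---|---|
| 100/100/100/100 | 37/36/38/38 | 16/15/16/16 | −5/−3/−3/−3 |
| 100/60/40/30 | 37/−4/−22/−32 | 16/−25/−44/−54 | −5/−43/−63/−73 |
| 100/150/200/250 | 37/86/138/188 | 16/65/116/166 | −5/47/97/147 |
| 0/50/100/150 | 0/49/101/151 | 0/49/100/151 | 0/51/102/151 |

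Without the covariate the model returns d_t, the raw difference, at every visit.

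**Would dropping Birth from the responses be enough?** No. With birth weight as covariate only, β is about 0.51, 0.80 and 1.06. A constant 100 g effect is then estimated at the later visits as about 49 to 51 g (low), 20 to 22 g (middle) and −4 to −5 g (high). The subtraction comes from conditioning on a value that treatment has changed, whether or not that value is also a response.

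**Treatment-by-visit test.** In 8 further simulated complete data sets of 1100 infants, the interaction coefficients, the interaction chi-square and the residual SD were identical with and without the covariate. Only the subject SD fell.

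**Mothers.** If the arms do not differ at Periconception, d_0 ≈ 0 and the week-20 and delivery estimates are d_t − β·0 = d_t. Only the Periconception row, (1 − β)·d_0, carries no information.

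**The case against.** The SAP never says that birth size is the infant covariate. Section 5.2.2 is one generic sentence covering infants and mothers, and it could be read as applying the covariate only where a pre-treatment value exists. That is fair: birth as covariate is an inference. But the sentence names infant weight as its first example and makes no exception. If the baseline means an enrolment value, the infant model cannot be fitted as written. Either way the text needs changing.

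It could also be said that growth conditional on birth size is a legitimate question. It is, but it is a different one from the between-arm difference planned in section 5.2, and it gives the Birth row no meaning.

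Several stronger readings are tempting and do not hold:

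- A reader might infer that infant growth effects are largely removed. Only the part already present at birth is subtracted; a difference arising later is kept in full (last row of the table).
- A reader might infer bias towards zero at every visit. With no effect at birth there is no bias, and with a fading effect the sign reverses.
- A reader might infer that the treatment-by-visit test is distorted. With complete data and a random intercept it is unchanged.
- A reader might infer that maternal gestational effects are lost. They are not when the arms are balanced at Periconception.
- A reader might want a single percentage lost. For a constant effect the loss runs from about 62% to more than 100% with the assumed correlation, and it is nil if nothing differs at birth.

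**Conclusion.** The point holds in this limited form. The baseline covariate is undefined and overlaps with response visits in Table 4. On the natural reading for infants, it conditions on an outcome that arises after randomisation. The Birth row then shows (1 − β)·d_0, and every later row is reduced by β·d_0.

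The form of the result rests on complete data, a random-intercept model and a common slope. The sizes in grams rest on assumed SDs, correlations and effect patterns, so they are illustrations and not predictions for this trial.

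The scope is secondary outcomes (13)–(15) and, to a lesser degree, the maternal-weight rows. The primary GEE analysis has no such covariate and is untouched. The change should be made, but the trial's main conclusion does not depend on it.

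**What to change.** In section 5.2.2, define the baseline separately for each outcome.

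- **Infant weight, length and BMI (13)–(15):** delete the baseline covariate. Fit treatment, visit and treatment × visit with the planned random effects, and keep Birth as a response visit.
- **Maternal weight:** choose one of two forms. Either keep the pre-pregnancy value as covariate and drop Periconception from the responses, or keep Periconception as a response with the arm means constrained equal at that visit.
- **Table 4:** amend to match. Under either maternal form, the Periconception row should show descriptive statistics only, with no arm difference.

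The cost is wording in the SAP and one table shell. No data collection, sample size or primary analysis changes.

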5.2.3. Analysis of count secondary outcomes

The count outcome will be summarised using number of subjects (n), number of events, incidence rate (events per 100 person-years) by intervention group, and will be analysed by a GEE model with treatment as fixed effect, centre as cluster effect, and follow-up time as offset. The distribution will be Poisson distribution and link function is log. Incidence rate ratio with their two-sided 95% CI between the two arms will be derived from the GEE model.

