2.2.2. Secondary outcomes

(1) The occurrence of fetus defects

- This is a composite outcome and will be defined as “occurred” if any of the 24 defects are detected by routine ultrasound screening during pregnancy (Details of defects types see Appendix 1).
- Time Frame: from the confirmation of pregnancy to before delivery.
- Type: binary variable (Yes / No).

(2) The occurrence of birth defects

- This is a composite outcome and will be defined as “occurred” if any of the 24 defects are detected by ultrasound examination within one year old (Details of defects types see Appendix 1).
- Time Frame: from birth to one year old.
- Type: binary variable (Yes / No).

(3) The occurrence of infant death or severe organ dysfunctions

- This is a composite outcome and will be defined as “occurred” if either infant death or severe organ dysfunctions occur.
- Time Frame: from birth to 6 months after delivery (can be expanding to the end of the 7th month).
- Type: binary variable (Yes / No).

(4) The occurrence of abortion that related with congenital defects

- Time Frame: from the confirmation of pregnancy to the 28th gestational week.
- Type: binary variable (Yes / No).

(5) Count of fetus defects, stillbirth, and birth defects

- Time Frame: from the confirmation of pregnancy to 28 days after birth.
- Type: Count-Number of events.

(6) Occurrence of confirmed congenital heart defects (CHD)

- All pregnancies will have prenatal ultrasound scans in the second trimester (around 20 to 24 weeks of gestation) performed by trained ultrasound sonographers; abnormal findings will be confirmed by authorized tertiary fetal medical centers. All newborns will have routine neonatal CHD screening, and those screened positive will be subsequently sent for further echocardiographic confirmation. The nomenclature of the International Paediatric and Congenital Cardiac Code (of the Nomenclature Working Group of the International Society for Nomenclature of Paediatric and Congenital Heart Disease) will be used to define CHD.
- Time Frame: from the confirmation of pregnancy to 28 days after birth.
- Type: binary variable (Yes / No).

(7) Occurrence of maternal gestational diabetes (GDM)

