2.2.3. Case ascertainment and case definitions

(1) Fetus and Birth defects

The examinations for detecting fetus and birth defects will follow the national routine usual care protocols. All fetus and birth defects identified from the 12 gestational weeks to 28 days after birth will be included. In consistent with the national birth defects surveillance policy, a total of 24 types of defects are defined (details of types of defects types see Appendix 1). Fetus defects will be detected by routine screening programs including prenatal DS screening, NT examination during gestational week 11 to 15, and ultrasound image examination during the second trimester (18-20 gestational week); and the number and type of birth defects after childbirth will be diagnosed and recorded according to national routine professional clinical examinations.

DS, caused by the trisomy, translocation, or partial trisomy of chromosome 21, is the most common genetic cause of intellectual disability. DS will be diagnosed by neonatologist. Neural tube defects including spina bifida and hypospadias, will be diagnosed by ultrasound examination and pediatric neurosurgeon.

CHD will be diagnosed by echocardiographic confirmation based on the local CHD screening policy (pulse oximetry plus cardiac murmurs). Hydrocephalus, digestive tract malformations, urinary malformations and other defects also will also be diagnosed either by ultrasound or some other specific diagnosis methods. From June 2016, a neonatal congenital heart defects screening policy has been issued in Shanghai city, the screening and diagnosis of CHD in neonates is embedded in this program following the routine protocols.

(2) *Abortion*

Abortion is defined as pregnancy suspension including miscarriage and artificial abortion. Detailed information for abortions will be collected, including time of abortion, reasons for abortion especially and antenatal information before abortion.

(3) *Pregnancy complications*

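### The count of defects and stillbirths is analysed per person-year with a follow-up-time offset, so the rate ratio can mix defect risk with pregnancy duration

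*SAP*

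**What the plan says.** Secondary outcome (5) in SAP section 2.2.2 is the "Count of fetus defects, stillbirth, and birth defects", recorded as "Type: Count-Number of events", with "Time Frame: from the confirmation of pregnancy to 28 days after birth".

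Section 5.2.3 summarises it as an "incidence rate (events per 100 person-years) by intervention group" and fits a Poisson, log-link "GEE model with treatment as fixed effect, centre as cluster effect, and follow-up time as offset". The effect measure follows from that: "Incidence rate ratio with their two-sided 95% CI between the two arms will be derived from the GEE model".

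Three other places bear on the offset:

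- Section 5.2.3 does not say when follow-up time starts or stops. Sections 2.2.1 and 2.2.2 open the window when pregnancy is confirmed. Sections 2.2.3 and 5.1.1 count defects from gestational week 12.
- Section 2.2.3 states: "Abortion is defined as pregnancy suspension including miscarriage and artificial abortion". An abortion therefore ends the pregnancy before the planned close of the window.
- Section 4.1 removes women whose primary outcome is missing, which forms the mITT population. Section 5.2 bases secondary analyses on the ITT population unless specified.

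The primary outcome (section 5.1.1) is analysed as a risk ratio per pregnancy, without person-time. No analysis of the count without the offset is planned.

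**The concern.** A log-time offset with its coefficient fixed at one assumes that expected events grow in proportion to time observed. That suits recurrent events such as infections. It does not suit a structural defect, which is present or absent in a pregnancy and is found at set points: early screening, the second-trimester scan and examination of the newborn. More weeks between those points do not add defects proportionally.

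Time observed is also not independent of the outcome. Stillbirth is one of the counted events and shortens the window, and termination after a diagnosed defect does the same. An early loss or a late confirmation of pregnancy shortens the denominator too, without changing the number of defects in proportion.

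The rate ratio is therefore the per-pregnancy ratio multiplied by the ratio of mean durations (control over experimental). At stake is whether outcome (5) answers the same question as the primary risk ratio over the same window. The two could differ because of the denominator alone, and part of secondary outcome (4), defect-related abortion, could enter the result for outcome (5).

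**Working it through.** Section 5.2.3 gives no figure to reproduce, so the check asks how far the offset can move the ratio.

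**Inputs from the SAP (section 3.5):** event proportions r0 = 0.08 (control) and r1 = 0.04 (experimental); 1100 women per arm.

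**Assumptions not in the SAP:** one event per affected pregnancy; follow-up cut at pregnancy loss; 38 weeks of full follow-up, 17 weeks if terminated for a defect, 4 weeks for an early loss; early losses carry no counted event.

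**Formula.** With offset, the rate in an arm is close to total events over total person-time. This is exact under an independence working correlation and approximate otherwise. For an arm with event proportion r, a share q of affected pregnancies terminated, and early loss l:

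T = r[17q + 38(1 − q)] + 4l + 38(1 − r − l)

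Rate ratio = (r1/T1)/(r0/T0) = (r1/r0) × (T0/T1)

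Without the offset the ratio is r1/r0 = 0.500.

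**Example, half of affected pregnancies terminated in both arms.** Mean duration of an affected pregnancy is 0.5 × 17 + 0.5 × 38 = 27.5 weeks.

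- T0 = 0.08 × 27.5 + 0.92 × 38 = 37.16
- T1 = 0.04 × 27.5 + 0.96 × 38 = 37.58
- Ratio = 0.5 × 37.16/37.58 = 0.494

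On the planned scale, 8 v 4 events per 100 pregnancies become 0.08 × 5200/37.16 = 11.2 v 0.04 × 5200/37.58 = 5.5 per 100 person-years.

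| Scenario (control v experimental) | T0 | T1 | Rate ratio |
|---|---|---|---|
| 8% v 4%; 50% v 50% terminated | 37.16 | 37.58 | 0.494 |
| 8% v 4%; 50% v 20% terminated | 37.16 | 37.832 | 0.491 |
| 8% v 4%; 20% v 50% terminated | 37.664 | 37.58 | 0.501 |
| 8% v 4%; 50% v 50% terminated; early loss 15% v 12% | 32.06 | 33.50 | 0.479 |
| 8% v 4%; 50% v 50% terminated; early loss 15% v 10% | 32.06 | 34.18 | 0.469 |
| 8% v 8%; equal terminations and losses | equal | equal | 1.000 |
| 8% v 8%; 50% v 20% terminated | 37.16 | 37.664 | 0.987 |

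The first row needs no difference in management between arms: fewer defects alone lengthen mean follow-up in the experimental arm. The third row shows that the direction can reverse.

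**Sensitivity to the durations.** With 37, 16 and 5 weeks in place of 38, 17 and 4, half terminated in both arms again gives 0.494. Adding early loss of 15% v 10% gives 0.470.

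**Size against precision.** Expected events are 0.08 × 1100 = 88 and 0.04 × 1100 = 44. Before clustering, the standard error of the log ratio is √(1/88 + 1/44) = 0.185. On the log scale the first two rows move the estimate by 0.011 and 0.018, at most about a tenth of a standard error. The 0.469 case moves it by 0.064, about a third.

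**The case against.** The strongest reply is that this hardly matters. It concerns one of 16 secondary outcomes, and section 7 has no table shell for it. Events over the same window are already analysed per pregnancy in the primary analysis, and the termination-only shift is far below sampling error. This stands, and it sets the weight of the point. It does not give a reason for the offset.

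Second, an offset allows, if crudely, for women followed only in part, and section 3.5 expects 10% dropout. This stands in part. Without an offset, a woman lost midway would count as fully observed with no event. The exclusion in section 4.1 largely deals with that, provided it is applied to this outcome.

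Third, follow-up time is undefined, so truncation at pregnancy loss is a plausible reading and not stated text. That is correct. If counting starts at week 12, or if early losses fall under the missing-outcome exclusion, much of the early-loss effect disappears.

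Some stronger readings are tempting but unsupported:

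- *The rate ratio is necessarily biased.* With no effect and equal durations it is exactly 1.
- *The offset always favours the experimental arm.* The direction follows whichever arm has the shorter pregnancies.
- *Affected women receive extra weight.* Each event still counts once; only the arm's total denominator shrinks.
- *The package will change terminations.* Section 3.3 describes expert consultation about treatment after birth "in the future to avoid unnecessary abortions", but its text places that pathway in both arms, while its table lists the consulting in the experimental column. These passages must be reconciled; until then, a difference in terminations is possible, not established.

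**Conclusion.** The point holds as a small defect in one secondary analysis. The offset is ill-suited to a count over a single bounded pregnancy, and the resulting rate ratio can depart from the per-pregnancy ratio whenever mean duration differs between arms, whether through a true effect or through different termination or loss rates.

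Under the assumed durations, departures of about 1% to 2% arise when terminations are equal or fewer in the experimental arm. The 4% to 6% departures (0.479 and 0.469) need early-loss differences of 3 to 5 percentage points, which the SAP does not give, and should not be taken as the expected size. The primary analysis is unaffected.

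**What to change.** In section 5.2.3, remove the follow-up-time offset. Keep the Poisson-log GEE with centre as cluster and state that the robust variance is used. Report events per 100 pregnancies in each arm and the ratio of mean counts per pregnancy with its 95% CI. State that the analysis set is the women with the outcome window ascertained, by the mITT rule of section 4.1, and say how early losses are classified under that rule.

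If person-time is kept, define its start and end, settle whether counting opens at confirmation of pregnancy or at week 12, and present it only as a sensitivity analysis.

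The cost is a few lines of SAP text and a changed unit. The small downside is that women with partial follow-up must be handled by the mITT exclusion, because the offset no longer allows for them. Their number should be reported by arm.
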